10.2.4. Fracture Event Diary

Subjects will be prompted report any new suspected fractures and asked to provide details about a fracture event including number, location, and date of suspected fracture(s) at time points specified in Table 3. Subjects will be asked about the impact of the fracture on physical function for up to 8 weeks from the report of a fracture event. When a new fracture event is reported in the diary, the study site will be notified and will follow up with the subject to collect additional details. Radiographs will be collected at the next scheduled visit to confirm the fracture. If radiographs were taken outside of study site, the site will attempt to collect these radiographs. Questions regarding baseline level of function will be administered at the beginning of the study to further assess the impact of fracture.

10.6. Safety Assessments

During the Observation Period, safety will be evaluated by the incidence and severity of AESI as well as the relationship of AESI to prior setrusumab. Incidence and severity of AESI as well as relationship of AESI to prior setrusumab treatment will also be collected via chart review for the Off-study Period between ASTEROID and the UX143-CL203 study. During the Retreatment and Extension Periods, safety will be evaluated by the incidence, severity, and relationship to setrusumab of TEAEs, AESIs, and treatment-emergent SAEs. Safety will also be assessed by changes from the First Visit during the Observation Period and the Retreatment Screening Visit

prior to entering the Retreatment Period to scheduled time points in vital signs, physical examination, focused neurological examination, audiometry, dental health evaluations, clinical laboratory evaluations, and ECGs. Safety will also be evaluated by the development of anti-setrusumab antibodies and pregnancy testing.

Safety definitions and instructions for assessing severity and causality are presented in Appendix 3.

Refer to Appendix 4 for instructions how to elicit, record, and report including collection period timeframes and timelines for AEs, SAEs, AESIs, pregnancies, other safety information and any urgent safety measures taken to protect the safety or welfare of subjects.

10.6.1. Adverse Events of Special Interest

AESIs for this study include the potential risks of ischemic cardiovascular events, infusion reactions and hypersensitivity, and neurologic sequelae associated with bone overgrowth. Medical Dictionary for Regulatory Activities (MedDRA) search strategies will be specified for AESIs in the Statistical Analysis Plan, and include standardized MedDRA queries, if available.

AESI will be collected from the time the subject signs the ICF and through the safety follow-up period and should be reported within 24 hours of site Investigator, designee or site personnel's knowledge of the event as outlined in Table 11.

10.6.2. General Medical History

General medical history will be collected during screening (Table 3). General medical information includes subject demographics and a history of major medical illnesses, diagnoses, and surgeries. Medical history also includes a chart review, including the collection of DXA and fracture events.

10.6.3. Vital Signs

Vital signs to be measured include seated systolic blood pressure and diastolic blood pressure, heart rate, respiration rate, and temperature. Vital signs will be measured after the subject has rested for at least 5 minutes, and prior to any other study assessments and drug administration.

10.6.4. Electrocardiograms

Single 12-lead ECG will be obtained using an ECG machine that automatically calculates the heart rate and measures PR, QRS, QT and (QTc) intervals. ECGs will be performed at timepoints indicated in the Schedule of Events (Table 3).

While conduction intervals provided by the ECG machine may be used, final interpretation of ECGs, including any rhythm abnormalities, will be made by an independent central vendor to ensure reliability and reproducibility. Any abnormalities will be recorded.

10.6.5. Safety Laboratory Tests

Blood and urine samples will be collected prior to administration of study drug, as specified in Table 3 and Table 4, and analyzed by a central laboratory. Fasting is required for visits that coincide with blood sample collection for CC (Table 3 and Table 4).

Study site personnel should indicate on relevant laboratory request documents if the subject is taking high dose biotin supplements (found in multivitamins, biotin supplements, and some supplements to support hair, skin and nail growth) due to potential risk of assay interference (eg, troponin) (FDA, 2019).

The safety laboratory evaluations to be performed in this study are listed in Appendix 1.

For any subject who experiences an SAE or other AE of concern, the Investigator (and/or Medical Monitor) may at his/her discretion perform additional laboratory tests for subject safety.

10.6.6. Pregnancy Testing

Female subjects of childbearing potential will have urine pregnancy tests at visits indicated in Table 3. Females not of childbearing potential are not required to undergo pregnancy testing. Refer to Appendix 2 for childbearing potential definitions.

Female subjects with a positive pregnancy test at Screening will not be enrolled in the study.

Additional pregnancy tests will be performed at any visit in which pregnancy status is in question. A serum pregnancy test will be performed in the event of a positive or equivocal urine pregnancy test result or can be performed if pregnancy test by urine is not feasible. For visits in which setrusumab is administered, blood and urine should be collected prior to drug administration.

Refer to Appendix 4 for pregnancy reporting requirements.

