- 12. History of or concomitant uncontrolled diseases such as hypo-/hyperparathyroidism, hypo-/hyperthyroidism, Paget's disease, abnormal thyroid function or thyroid disease or other endocrine disorders or conditions that could affect bone metabolism eg, Stage IV/V renal disease
- 13. A history of rickets or osteomalacia or any skeletal condition (other than OI) leading to long-bone deformities and/or increased risk of fractures
- 14. Documented alcohol and/or drug abuse within 12 months prior to dosing or evidence of such abuse as indicated by the laboratory results during the screening/baseline assessments

15. Documented history of significant psychiatric or medical disorder that would prevent the participant complying with the requirements of the protocol or would make it unsafe for the participant to participate in the study as judged by the investigator

- 16. Current/previously reported allergy to the study drug or any of its excipients or the class of drug under investigation
- 17. History of external radiation

Study Interventions

Table 2: Study Interventions

Intervention	Setrusumab
Dose Formulation	mg lyophilized powder for solution
Unit Dose Strength(s)/Dosage Level(s)	20 to 40 mg/kg QM CCI
Route of Administration	60-minute IV infusion
Use	Experimental

^a The dosing strategy in the Retreatment and Extension Periods will be based on the pharmacokinetic (PK) and serum bone turnover marker data from the Phase 2b ASTEROID study and the Phase 2 Period of the UX143-CL301 study. The selected dose will be in the range of 20 to 40 mg/kg CCl

IV, intravenous CCI; QM, once a month.

Duration of Subject Participation

Screening may take up to 1 month. The Observation Period is expected to take up to 18 months. The Retreatment Period is 12 months. The Extension Period continues for at least 12 months or until setrusumab is commercially available in a subject's given region.

Assessments

Assessments and associated timing are provided in Table 3

Table 3: Schedule of Events

	screening		Screening Observation Period ^a		Retx Period (Month) ^a														
	-4 to -1 vks prior First Visit	First Visit ^b	CC Visits, CC between the First Visit & Retx Period	Retx Scrn Visit, -4 to -1 wks prior to Retx BL ^c	0 (Retx BL)	1	2	3	4	5	6	7	8	9	10	11	12	Ext Per ^a	EOS/ ET ^d
Informed Consent	X																		
Inclusion/Exclusion	X			X															
Medical History ^e	X																		
Urine Pregnancy Test	X			X															

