7.1.3. Rationale for Study Design

The purpose of this study is to further investigate the safety and efficacy of setrusumab in adults with OI. The Phase 2b study (ASTEROID; MBPS205) demonstrated clinically meaningful, dose-dependent increases in BMD over the course of 12 months of setrusumab, with discontinuation of therapy resulting in partial loss of BMD gains over the next 12 months. The proposed study will re-recruit these subjects to monitor the long-term effects off-setrusumab and to evaluate the effect of setrusumab retreatment. The potential inclusion of up to 112 subjects treated with open-label setrusumab for up to 2 years will augment the current safety and efficacy database. These results will help inform longer-term treatment strategies in adults with OI, a chronic disease for which no therapy is currently approved globally. Additionally, retreating these adults with OI will provide insight into the effects of stopping and restarting treatment with setrusumab, potentially with and without interim bisphosphonate use, and help characterize long-term safety with setrusumab treatment.

The proposed study is divided into multiple parts which each have their own goal. During the Observation Period, data will be collected to evaluate setrusumab off-treatment effects. Additional data will be collected from the Off-Study Period via chart review to provide additional information on post-setrusumab effects that occurred prior to enrollment into the Observation Period. The Observation Period visits will occur at intervals relative to the Phase 2b study. The effects of initial setrusumab dose-level and zoledronic acid administration post-setrusumab will be further elucidated, with specific evaluation of changes in BMD and fracture rate over time. Together, data collected from the Off-Study and Observation Periods provide a long-term view of the effects of setrusumab discontinuation in adult OI.

The Retreatment Period will evaluate the efficacy and safety of 12 doses of open-label setrusumab QM. Retreatment may provide additional insights into the effects of setrusumab in subjects that previously received setrusumab. The potential impact of how subjects were treated in the original Phase 2b study (initial setrusumab dose-level and/or zoledronic acid

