8.1. Inclusion Criteria

Subjects who participated in ASTEROID were ages 19 to 74 years at the time of enrollment. Eligible individuals must meet all of the following criteria:

- 1. Males or females who participated in the Phase 2b ASTEROID study
- 2. Females of childbearing potential must consent to use highly effective contraception (Appendix 2) during the Observation, Retreatment, and Extension Periods through 2 months after the last dose of setrusumab and agree not to become pregnant. Provide informed consent after the nature of the study has been explained, and prior to any research-related procedures

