9.5. Treatment Assignment

9.5.1. Treatment Assignment

This is an open-label study. No study drug is provided during the Observation Period. During the Retreatment Period, all subjects will receive the same dose of setrusumab administered QM. During the Extension Period, subjects will be randomized 1:1 to either continue treatment with open-label setrusumab QM or transition to open-label setrusumab CCI. For the Extension Period dosing groups, randomization will be stratified by OI type (I vs III/IV). Randomization will be completed using interactive response technology (IRT).

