APPENDIX 4. ADVERSE EVENT COLLECTION, ELICITING, RECORDING AND REPORTING

Collection Period & Reporting Timeframe: Adverse Event & Other Safety Information Reporting

Table 11: Collection Period and Reporting Timeframes for Adverse Event and Other Safety Information Reporting

Event Type	Collection Period	Reporting Timeframe	Report to:
Serious Adverse Event (SAE)	Start: From the time the subject signs the ICF End: Two months after the final administration of study drug	Report all SAEs within 24 hours of site Investigator, designee or site personnel's knowledge of the event.	Electronic Data Capture (primary) Ultragenyx (back-up if Electronic Data Capture is down or not available) email: [contact] [contact]
Adverse Event (AE)	Start: From the time the subject signs the ICF End: Two months after the final administration of study drug	Report all non-serious AEs within a target of 3 business days of site Investigator, designee or site personnel's knowledge of the event.	Electronic Data Capture
Treatment- emergent adverse events (TEAEs)	Start: From the time the subject signs the ICF End: Two months after the final administration of study drug	Report all non-serious TEAEs within a target of 3 business days of site Investigator, designee or site personnel's knowledge of the event.	Electronic Data Capture
Pregnancy (includes Partner pregnancy)	Start: From the time the subject signs the ICF End: Two months after the final administration of study drug	Report all pregnancies within 24 hours of site Investigator, designee or site personnel's knowledge of the event	Electronic Data Capture (primary) Ultragenyx (back-up if Electronic Data Capture is down or not available) email: [contact] [contact]
Adverse Events of Special Interest (AESI)	Start: From the time the subject signs the ICF End: Two months after the final administration of study drug	Report all AESI within 24 hours of site Investigator, designee or site personnel's knowledge of the event.	Electronic Data Capture (primary) Ultragenyx (back-up if Electronic Data Capture is down or not available) email: [contact] [contact]

Table 12: Safety Contact Information

Global Drug Safety & Pharmacovigilance Serious Adverse Events, Adverse Events of Special Interest, and Pregnancy Reporting		Medical Monitor
Email: [contact]	PPD	, MD, MS
[contact]	PPD	
	PPD	

Eliciting Adverse Events

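### The Table 3 pregnancy-test row schedules no urine test from the first setrusumab dose onward; unless the Urinalysis row or Table 4 schedules one, an unsuspected pregnancy on treatment would be found only by a for-cause test

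*Combined protocol and SAP*

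**What the plan says.** Section 10.6.6 delegates the timing of tests to the schedule of events: "Female subjects of childbearing potential will have urine pregnancy tests at visits indicated in Table 3". In Table 3 (Synopsis) the row labelled "Urine Pregnancy Test" carries a mark at Screening and a mark at Retreatment Screening, and no others.

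Beyond that schedule, Section 10.6.6 provides two things. One is a for-cause test: "Additional pregnancy tests will be performed at any visit in which pregnancy status is in question". The other is a serum test, used after a positive or equivocal urine result or when urine testing is not feasible. On enrolment it adds: "Female subjects with a positive pregnancy test at Screening will not be enrolled in the study".

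The surrounding obligations last much longer than the marked tests:

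- Section 8.1 requires highly effective contraception "during the Observation, Retreatment, and Extension Periods through 2 months after the last dose of setrusumab and agree not to become pregnant".
- Appendix 4, Table 11 collects pregnancies until 2 months after the final dose and instructs sites: "Report all pregnancies within 24 hours of site Investigator, designee or site personnel's knowledge of the event".
- Section 7.1.3 describes Retreatment dosing: "The Retreatment Period will evaluate the efficacy and safety of 12 doses of open-label setrusumab QM".
- In the Extension, under Section 9.5.1, "subjects will be randomized 1:1 to either continue treatment with open-label setrusumab QM or transition to open-label setrusumab" on a regimen that is redacted. The Synopsis gives the Extension a minimum of 12 months.

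**The concern.** The protocol treats fetal exposure as something to prevent, through contraception, and to capture, through 24-hour reporting. The reporting clock starts when the site learns of a pregnancy. In the row that governs testing, nothing scheduled after Retreatment Screening would produce that knowledge. A for-cause test needs someone to be suspicious first. A site following the row as printed would dose a woman of childbearing potential for two years or more with no routine check, including none on the day of the first dose.

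At stake is the number of doses given to a woman whose pregnancy is not yet recognized, and a late or missed report when an unrecognized pregnancy is present at EOS/ET. Testing does not change how many pregnancies occur; it shortens exposure.

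**Working it through.** **Reading the row.** The plan gives no figure to reproduce, so the first check is of the table itself. Table 3 has 19 visit columns: Screening, First Visit, the periodic Observation visits, Retreatment Screening, Months 0 to 12 (13 columns), Extension, and EOS/ET. The pregnancy row has 19 cells. So do the Inclusion/Exclusion, Drug Administration and Vital Signs rows, which confirms the alignment and makes a lost cell unlikely.

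| Row | Marked visits |
|---|---|
| Urine pregnancy test | Screening; Retreatment Screening |
| Drug administration | Months 0-12; QM in the Extension |

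Of the 13 Retreatment dosing visits, 0 carry a pregnancy-test mark. The Extension and EOS/ET also carry none.

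**Length of the untested span.** Take a woman on QM dosing through the minimum 12-month Extension, from Retreatment Screening to the end of the pregnancy reporting window.

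- Low: 1 week (0.23 months) + last dose at Month 23 + 2 months = 25.2 months.
- High: 4 weeks (0.92 months) + last dose at Month 24 + 2 months = 26.9 months.
- Doses in the span: 12 + 12 = 24 using Section 7.1.3, or 13 + 12 = 25 using the Table 3 marks. The redacted Extension regimen may give fewer.

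**Exposed doses per pregnancy.** The documents do not give these inputs, so they are assumptions: recognition without testing T = 6, 10 or 14 weeks after conception; urine test positive from 2 weeks; conception uniform over the dosing cycle. The dose interval is D = 52.18/12 = 4.35 weeks.

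- No routine test: T/D.
- Test before every third dose: a tested dose is given only if conception was under 2 weeks earlier. The next dose is given if conception was under min(T, D + 2) weeks earlier, and the one after that if under min(T, 2D + 2). The mean is [2 + min(T, D + 2) + min(T, 2D + 2)] / 3D, with D + 2 = 6.35, 2D + 2 = 10.70 and 3D = 13.04.

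| T (weeks) | No test | Every third dose | Averted |
|---|---|---|---|
| 6 | 6/4.35 = 1.38 | (2 + 6 + 6)/13.04 = 1.07 | 0.31 |
| 10 | 10/4.35 = 2.30 | (2 + 6.35 + 10)/13.04 = 1.41 | 0.89 |
| 14 | 14/4.35 = 3.22 | (2 + 6.35 + 10.70)/13.04 = 1.46 | 1.76 |

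For comparison, a test before every dose leaves 2/4.35 = 0.46 exposed doses, averting 0.92, 1.84 or 2.76.

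**Across the trial.** Assume n = 20, 30 or 50 women of childbearing potential and r = 0.5% or 1% pregnancies per year over 2 years. Expected pregnancies are 2 × n × r.

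| Case | Pregnancies | Averted, every third dose | Averted, every dose |
|---|---|---|---|
| Low (20; 0.5%; 6 weeks) | 0.2 | 0.2 × 0.31 = 0.06 | 0.2 × 0.92 = 0.18 |
| Central (30; 1%; 10 weeks) | 0.6 | 0.6 × 0.89 = 0.54 | 0.6 × 1.84 = 1.10 |
| High (50; 1%; 14 weeks) | 1.0 | 1.0 × 1.76 = 1.76 | 1.0 × 2.76 = 2.76 |

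The 1% rate is the ceiling in Appendix 2's definition of highly effective contraception with consistent and correct use. The totals scale in proportion to the rate.

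**The case against.** The strongest reply is that on-treatment tests may be scheduled where this copy cannot be read. Table 10 lists a pregnancy test, if applicable, in its Urinalysis column. Section 10.6.5 collects urine before dosing under Tables 3 and 4 and refers to Appendix 1 for the evaluations. The Urinalysis marks and Table 4 are not visible. Section 10.6.6 also asks for blood and urine before drug at dosing visits, a sentence with little purpose in that section unless some tests fall at such visits. A reader might infer from the two-mark row that the plan has no routine on-treatment test at all; the documents do not support that as a flat statement. What survives is narrower. Section 10.6.6 names Table 3 alone, Table 3 has its own pregnancy row, Table 10 gives no timing, and the pre-dose sentence sets the order of collection without scheduling a test. If the tests exist elsewhere, the row that sites will consult is still incomplete.

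A reader might also infer that a positive test on treatment has no consequence. That is not so: any positive or equivocal urine result triggers a serum test, Appendix 4 requires reporting and follow-up to outcome, and Section 8.3.2 lets the Investigator withdraw a subject for safety. Only an explicit instruction to hold or stop dosing is missing from the visible text.

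It is fair, too, that safeguards exist (contraception, frequent visits with adverse-event questioning, a mandatory for-cause test), that the benefit is small, and that no visible text sets a testing frequency that the plan breaches. These points argue for a modest remedy. In the central case, testing at every dose would take 750 to 780 tests (25 or 26 per woman × 30) to avert 1.10 exposed doses, so that frequency is hard to defend.

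**Conclusion.** The concern holds in conditional form. The governing row schedules no test at Retreatment Baseline, Months 1-12, the Extension or EOS/ET. Unless the Urinalysis marks or Table 4 fill that gap, an unsuspected pregnancy would go untested for about 25 to 27 months, counting the 2 months after the last dose.

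The size is modest: about 0.06 to 1.8 exposed doses averted with testing every 3 months, centrally about 0.5. This rests on assumed numbers of women, pregnancy rates, recognition times and test sensitivity. The severity of fetal harm per exposed dose cannot be judged here, because reproductive toxicity data sit in the Investigator's Brochure. The case for change rests on low cost and on consistency with the protocol's own contraception and reporting window. Confidence is medium because of the unseen tables.

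**What to change.** First check whether the Urinalysis row or Table 4 already schedules on-treatment tests. If so, copy those marks into the Table 3 pregnancy row. If not, add marks there, for women of childbearing potential, at:

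- Retreatment Baseline, before dosing;
- existing dosing visits at least every 3 months;
- Month 12, before Extension randomization;
- EOS/ET. This last test averts no doses but serves the reporting window.

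As supporting text in Sections 10.6.6 and 8.3.1, state that a positive or equivocal urine result withholds the dose until the serum test already required is negative, and that confirmed pregnancy stops dosing, with follow-up under Appendix 4.

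Cost over the minimum Extension: 9 tests (Months 0, 3, ..., 24) + 1 at EOS/ET = 10 per woman, or 300 for an assumed 30 women with no dropout. Each further Extension year adds 12/3 = 4 per woman. Apart from two sentences of text, the downside is an occasional false positive that delays a dose until the serum result. No endpoint, sample size or visit changes.

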10.6.7. Concomitant Medications

Medications (investigational, prescription, over the counter, and herbal supplements) and nutritional supplements taken during the 30 days prior to Screening will be reviewed and recorded at the Screening visit. Use of any concomitant medications during the study should be recorded on the CRF. All concomitant medications will be coded according to the WHODrug Dictionary.

Site personnel should record date the medication was taken, the name of the medication, medication dosage, formulation, route of administration and the reason the medication was taken.

